6.4.6 Time period for collection of adverse events

All serious adverse events must be reported to the Coordinating Center within 1 business day after the investigator becomes aware of the event.

Follow-up of unresolved adverse events

Follow-up information is sent to the same contact(s) to whom the original SAE Report Form was sent, using a new SAE Report Form stating that this is a follow-up to the previously reported SAE and giving the date of the original report. Each re-occurrence, complication, or progression of the original event should be reported as a follow-up to that event regardless of when it occurs. The follow-up information should describe whether the event has resolved or continues, if and how it was treated, and whether the patient continued or withdrew from study participation.

7. BIOLOGICAL SAMPLING PROCEDURES

7.1 Solid Tumor Biopsy Samples

Patients who opt to undergo the optional biopsy and have tumors amenable to safely consider research biopsy, as determined by interventional radiology, will undergo a biopsy after signing consent and before initiation of study drug.

Patients who opt for the 2nd optional biopsy at the end of study participation will undergo the 2nd biopsy upon progression of disease or discontinuation of study drug due to any other reason (e.g. unacceptable toxicity, discontinuation of study drug at physician discretion, discontinuation of study drug at patient request).

Patients may opt to have the optional biopsy at the beginning of the study only, at the end of the study only, or both. Therefore, patients who decided against the optional biopsy at the beginning of the study may still opt to have the 2nd biopsy at the end of the study only, and should be encouraged by the local PI to do so.

When patients opt to have the optional biopsy, there will be 2-3 core biopsies obtained. Two of these cores will be paraffin embedded. One core will be sent for MammoSeq testing, which will include ESR assessment as well as other genes described above.

The other core will be used for the NanoString studies. A 3rd core, if obtained, will be banked as fresh frozen to be used in the event that the 2 other core biopsy samples do not contain enough usable tissue.

The core for MammoSeq will be performed as specified in the Laboratory Manual.

Leftover Samples

Any leftover study blood and tissue samples will be stored at **Magee-Womens Hospital Tissue Bank** or the **Magee-Womens Research Institute**. Samples will be de-identified and stored indefinitely. At enrollment, patients will have the option to allow that these samples be used in future research, given that consent for such is signed.

The study coordinator will keep a tumor sample log that includes the study number, a specimen serial number, the patient's name, time point in therapy, and the date and time that the sample was drawn. The sample will be labeled with a serial number only. The laboratory technician will keep a log with the specimen number, conditions, processing and storage information.

Note: The correlative sample collection schedules outlined above are based on an ideal subject. The sample schedule should be followed as closely as is realistically possible; however, the schedule may be modified due to problems such as scheduling delays or conflicts (e.g., clinic closure, poor weather conditions, vacations, etc).

7.2 Blood Samples

Peripheral blood will be collected for 2 purposes: laboratory monitoring of adverse event, and analysis of ESR1 mutation presence and frequency. The volume of blood required for each collection is 10mls, and 40mls respectively. The blood sample for monitoring adverse events

will be sent to the center's laboratory. Blood specimens for determination of the presence of ESR1 mutation in circulating tumor DNA by ddPCR will be drawn into 4- 10ml collection tubes, and store at ambient temperature. They will be delivered to the laboratory as specified in the Laboratory Manual within 3 days. In the laboratory, ctDNA and genomic DNA will be isolated and stored at -20°C , as described in the Laboratory Manual. These samples will be analyzed for ESR ctDNA internally and for dd PCR and NGS for other genes of potential interest in collaboration with AstraZeneca.

The study coordinator will keep a blood sample collection log that includes the study number, a specimen serial number, the patient's name, time point in therapy, and the date and time that the sample was drawn. The sample will be labeled with a serial number only. The laboratory technician will keep a log with the specimen number, conditions, processing and storage information.

The correlative sample collection schedules outlined above are based on an ideal subject. The sample schedule should be followed as closely as is realistically possible; however, the schedule may be modified due to problems such as scheduling delays or conflicts such as clinic closure, poor weather conditions, vacations, etc.

7.3 Leftover Samples

Any leftover study blood and tissue samples will be stored at **Magee-Womens Hospital Tissue Bank** or the **Magee-Womens Research Institute**. Samples will be de-identified and stored indefinitely. At enrollment, patients will have the option to allow that these samples be used in future research given that consent for such is signed.

7.4 Handling, storage and destruction of biological samples

Peripheral blood obtained for study monitoring of side effects and for analysis of ctDNA will be sent to the center's laboratory as described in section 7.2 and the Laboratory Manual. Remaining samples after analysis will be stored under the supervision of [name] if the patient has agreed and signed informed consent allowing tissue storage.

7.5 Withdrawal of informed consent for donated biological samples

If any subject withdraws consent for donated biological samples, no further biological samples will be obtained. Of note, the case will still be included in the intention-to-treat analysis given that the subject has received at least one dose of the study compound. The obtained tissue will be analyzed, unless the patient has requested during study consent that all samples are destroyed.

8. ETHICAL AND REGULATORY REQUIREMENTS

8.1 Ethical conduct of the study

This study must be carried out in compliance with the protocol and Good Clinical Practice, as described in:

1. ICH Harmonized Tripartite Guidelines for Good Clinical Practice 1996.
2. US 21 Code of Federal Regulations dealing with clinical studies (including parts 50 and 56 concerning informed consent and IRB regulations).
3. Declaration of Helsinki, concerning medical research in humans (Recommendations Guiding Physicians in Biomedical Research Involving Human Subjects, Helsinki 1964, amended Tokyo 1975, Venice 1983, Hong Kong 1989, Somerset West 1996).

The investigator agrees to adhere to the instructions and procedures described in it and thereby to adhere to the principles of Good Clinical Practice that it conforms to.

8.2 Ethics and regulatory review

- Institutional Review Board: Information regarding study conduct and progress will be reported to the Institutional Review Board (IRB) per the current institutional standards of each participating center.
- Food and Drug Administration (FDA): This trial does not involve an Investigational New Drug (IND) application and no reporting is required with regards to the clinical trial outlined at this time.

8.3 Informed consent

An investigator will explain to each subject the nature of the study, its purpose, procedures involved, expected duration, potential risks and benefits. Each subject will be informed that participation in the study is voluntary and that she/he may withdraw from the study at any time, and that withdrawal of consent will not affect his/her subsequent medical treatment. This informed consent will be given by means of a standard written statement and will be submitted for IRB approval prior to use. No patient will enter the study before informed consent has been obtained. In accordance with the Health Information Portability and Accountability Act (HIPAA), the written informed consent document (or a separate document to be given in conjunction with the consent document) will include a subject authorization to release medical information to the study sponsor and supporting agencies and/or allow these bodies, a regulatory authority, or Institutional Review Board access to subjects' medical information that includes all hospital records relevant to the study, including subjects' medical history.

8.4 Changes to the protocol and informed consent form

Any change or addition to the protocol can only be made in a written protocol amendment that must be approved by AstraZeneca, Health Authorities where required, and the IRB/IEC/REB. Only amendments that are required for patient safety may be implemented prior to IRB/IEC/REB approval. Notwithstanding the need for approval of formal protocol amendments, the investigator is expected to take any immediate action required for the safety of any patient included in this study, even if this action represents a deviation from the

protocol. In such cases, AstraZeneca and IRB/IEC at the study site should be notified of this action in accordance with local IRB requirements.

8.5 Audits and inspections

Source data/documents must be available to inspections by AstraZeneca designee or regulatory health authorities.

9. STUDY MANAGEMENT

9.1 TABLE 4. Study timetable and end of study

Procedure	Screening ^a	Visit 1	Every 4 weeks	Every 8 weeks	Off Treatment	Follow Up
INFORMED CONSENT	X					
CLINICAL ASSESSMENTS						
Physical Exam	X	X	X ^b		X	X ^c
Medical History	X	X				X ^c
Vital Signs, Height, Weight	X	X ^d	X		X	(X)
ECOG Performance Status	X	X	X		X	
LABORATORY TESTS:						
Hematology (CBC with diff, platelets)	X	X ^e	X ^f		(X)	
Chemistries and liver function tests ^g	X	X ^e	X ^f		(X)	
PT, INR, PTT ^q	X					
Estradiol ^h	X					
Pregnancy Test ⁱ	X			X		
IMAGING:						
CT Chest/Abd/Pelvis ^j	X ^j			X	(X)	(X)
Brain MRI	X ^k				(X)	(X)
TREATMENT:						
Tamoxifen		X ^L				
Fulvestrant		X	X ^L			
Palbociclib		X ^P				

OTHER ASSESSMENTS:						
Concomitant Medication Review	X	X	X		X	
Symptom/Toxicity Assessment	X	X	X		X ^m	
Follow-up/Survival					X ⁿ	X ^c
CORRELATIVE STUDIES						
Blood collection for ESR1-mt analyzed by ct-DNA	X		X		X	
Archived tissue sample (from breast primary)	X					
Optional Solid Tumor Biopsy	X ^o				X ^o	

- a) Screening assessments are required within 28 days of initiation of treatment unless otherwise noted.
- b) Required ≤ 1 day prior to each specified treatment (exceptions may be made to extend this window, with approval by the Protocol Chair/designee).
- c) To continue until patient death
- d) Height at baseline only
- e) Required ≤ 14 days prior to first day of treatment; baseline labs may be used if within window.
- f) Required ≤ 1 day prior to each specified treatment (exceptions may be made to extend this window, with approval by the Protocol Chair/designee).
- g) Chemistries to include measurement of sodium, potassium, chloride, CO₂, BUN, creatinine, glucose, total bilirubin, calcium, total protein, albumin, AST, ALT, and alkaline phosphatase.
- h) Estradiol if required to determine post-menopausal status can be performed any time prior to Visit 1 treatment
- i) Serum Pregnancy test is required for women of childbearing potential only. Required ≤ 7 days prior to first treatment (i.e., day 1) unless otherwise noted. All outcomes of pregnancy should be reported to the PI and AstraZeneca.
- j) PET/CT is allowed and the choice between using a CT or PET with CT will belong to the treating physician. If a PET is chosen, the CT is mandatory and must be of diagnostic quality.
- k) Only if known CNS metastasis
- L) Fulvestrant will be dosed as follows: 2x250 mg injections on days 1, 15, 29, then next in 4 weeks (day 57) and continuing every 4 weeks thereafter. Tamoxifen will be dosed as follows: Tamoxifen 20mg PO Daily.
- m) All subjects must have a final toxicity assessment at least 30 days following the last dose of study drug
- n) Subjects will be followed approximately every 3 months after completion of study treatment for disease status and survival until death through clinic visit, phone call or record review.

- o) Optional tumor biopsy will be performed \leq 30 days prior to first day of treatment and within 30 days of treatment discontinuation.
- p) Palbociclib will be dosed 125mg PO QD days 1-21 of 28 day cycle
- q) PT, INR, PTT only needs to be repeated for optional biopsies if the patient on anticoagulants

(X) = OPTIONAL

Note: Additional tests may be performed at the discretion of the treating investigator as clinically indicated. The sample collection schedules outlined above are based on an ideal subject. The sample schedule should be followed as closely as is realistically possible; however, the schedule may be modified due to problems such as scheduling delays or conflicts (e.g., clinic closure, poor weather conditions, vacations, etc.).

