5.3 Restrictions and concomitant therapies during the study

The following restrictions apply during the entire duration of the study:

1. No other investigational therapy is allowed during the study period. If an investigational therapy was used prior to study enrollment, a washout period of 28 days is required before enrollment.
2. No anticancer agents other than the study medications may be given to patients during the study period, with the following exceptions:
 1. Bisphosphonates, Zometa (zoledronic acid), or Xgeva (Denosumab)
 2. GnRH analog agents.
3. If any other anticancer agents are required for a patient then the patient must first be withdrawn from the study.
4. Concurrent radiation therapy is prohibited, however palliative radiotherapy may be considered on a case by case basis after discussion with the Study Chair.
5. Grapefruit and other citrus juices affect P450 and PgP activity. Concomitant use will be avoided. All CYP3A4 inducers and inhibitors should be avoided.
6. Medications that inhibit or induce CYP2D6, CYP2C8/9 and CYP2D6 will be avoided and used at the discretion of the principal investigator or treating physician on a case by case basis. Please see appendix A for a list of these medications.
7. Anticoagulant medications can be used during the study period. The appropriate PT, INR and PTT levels will be determined at the discretion of the treating physician.

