5.6 Procedures for discontinuation of a subject from treatment

All patients who initiate protocol treatment will be included in the overall evaluation of response as part of the ITT analysis. All reasons for discontinuation of treatment should be documented clearly in the study record. In case of treatment discontinuation due to unacceptable toxicity as defined in section 6.4, the patients will still be included in the overall evaluation of response by ITT. If the study medication is discontinued at the patient's own request, the reason for discontinuation from the study must be documented and the patient followed for outcomes by ITT analysis.

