6.3 Efficacy

Response and progression will be evaluated in this study using the international criteria proposed by the revised Response Evaluation Criteria in Solid Tumours (RECIST) Committee (version 1.1). Changes in only the largest diameter (unidimensional measurement) of the tumor lesions are used in the RECIST criteria. Patients will be evaluated for response after every 2 cycles of therapy. In the case of non-measurable disease (as defined in 6.3.2), progression of disease will be determined by the appearance of new metastatic lesions or clinical worsening secondary to the non-measurable metastatic site at the treating physician's discretion.

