- Complete Response (CR): Disappearance of all non-target lesions and normalisation of tumor marker level. All lymph nodes must be non-pathological in size (<10mm short axis).
- Non-CR/Non-PD: Persistence of one or more non-target lesion(s) and/or maintenance of tumor marker level above the normal limits.
- Progressive Disease (PD): Unequivocal progression of existing non-target lesions. (Note: the appearance of one or more new lesions is also considered progression).

Evaluation of Best Overall Response

The best overall response is the best response recorded from the start of the treatment until disease progression/recurrence (taking as reference for progressive disease the smallest measurements recorded since the treatment started). The patient’s best overall response assignment will depend on the findings of both target and non-target disease and will also take into consideration the appearance of new lesions.

TABLE 2. Time to response definition

Target Lesions	Non-Target Lesions	New Lesions	Overall Response
-----------------------	---------------------------	--------------------	-------------------------

CR	CR	No	CR
CR	Non CR/Non PD	No	PR
CR	Not evaluated	No	PR
PR	Non PD or not all evaluated	No	PR
SD	Non PD or not all evaluated	No	SD
Not all evaluated	Non PD	No	NE
PD	Any	Yes or no	PD
Any	PD	Yes or no	PD
Any	Any	Yes	PD

CR= complete response, PR= partial response, PD= progressive disease, SD= stable disease, NE= not evaluable.

Note: Patients with a global deterioration of health status requiring discontinuation of treatment without objective evidence of disease progression at that time should be reported as “*symptomatic deterioration*”. Every effort should be made to document the objective progression even after discontinuation of treatment.

Progression Free Survival

PFS is defined as the duration of time from time of randomization to time of progression or death, whichever occurs first. PFS for a subject without an event will be censored on the date of last tumor assessment. If an interval of 6 months passes without a tumor assessment, PFS will be censored at the time of the earlier tumor assessment, even if an event (progressive disease or death) is later observed.

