11. EVALUATION AND CALCULATION OF VARIABLES

11.1 Calculation or derivation of efficacy variable(s)

The primary objectives of the study are descriptive assessments of ESR1 mutation detection in plasma. One of the secondary endpoints of the study is PFS. PFS is defined as the duration of time from time of randomization to time of progression or death, whichever occurs first. PFS for a subject without an event will be censored on the date of last tumor assessment. If an interval of 6 months passes without a tumor assessment, PFS will be censored at the time of the earlier tumor assessment, even if an event (progressive disease or death) is later observed. If a patient has not had an event, PFS will be censored at the date of the last adequate tumor evaluation. PFS will also be censored at the date of tumor evaluation when the next tumor evaluation (or death) is >6 months after the previous evaluation without an event. PFS will be assessed via local radiology assessment according to RECIST 1.1.

Although central review may occur as part of site calibration or an audit, the local assessment will be considered as the basis for the primary efficacy analysis. In the absence of measurable disease at baseline, the following criteria (per RECIST 1.1) will be used to assess disease progression among the patients with nonmeasurable lytic or mixed (lytic + blastic) bone lesions: 1) The appearance of one or more new lesions or 2) Unequivocal progression of existing non-measurable lesions.

Additional secondary endpoints include response rate, clinical benefit rate, (defined as CR+PR+ SD at any tumor assessment), clinical benefit rate at 6 months (CBR6), in the entire cohort, and the ESR1-mut cohorts. Response rate will be reported from best overall response according to RECIST 1.1 and as described in section 6.3. The response rate will then be compared amongst the tamoxifen plus palbociclib and fulvestrant plus palbociclib arms in the entire cohort and in the subgroup of ESR1-mt patients.

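### Patients who stop treatment without progression have no required tumor assessments, so by default their PFS is censored at the last scan

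*Combined protocol and SAP*

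**What the plan says.** **Schedule.** In Section 9.1, Table 4, the row "CT Chest/Abd/Pelvis" is mandatory at screening and every 8 weeks. In the Off Treatment and Follow Up columns it carries the bracketed mark that the key defines as optional. Footnote n has subjects followed about every 3 months after treatment for "disease status and survival until death through clinic visit, phone call or record review". Section 6.3 ties response evaluation to treatment: "Patients will be evaluated for response after every 2 cycles of therapy". The follow-up item in Section 6.2 lists only disease status and survival.

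**Endpoint.** Section 11.1 states: "PFS is defined as the duration of time from time of randomization to time of progression or death, whichever occurs first". It adds: "PFS will be assessed via local radiology assessment according to RECIST 1.1". A subject without an event is censored at the last tumor assessment. An event that follows a gap of more than 6 months without assessment is not counted, and the subject is censored at the earlier assessment (Sections 6.3.4 and 11.1).

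**Intent after stopping.** Section 5.5 allows stopping for toxicity, patient request or physician discretion. Section 5.6 keeps these patients in the ITT evaluation and wants "the patient followed for outcomes by ITT analysis" when the patient asks to stop. Section 5.8 censors at study withdrawal only when the patient refuses all follow-up. The note on symptomatic deterioration in Section 6.3.4 says: "Every effort should be made to document the objective progression even after discontinuation of treatment".

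**Use.** Section 12.1 calls fulvestrant promising if the fitted PFS hazard ratio is below 0.8 (unselected population) or below 0.65 (ESR1-mutant).

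**The concern.** The plan intends to follow patients to progression after they stop treatment, but its schedule requires no radiology for them. A patient who stops for toxicity, by request or with symptomatic deterioration can leave the PFS risk set at the last on-treatment scan although the event follows soon after. If the reason for stopping is related to prognosis, that censoring is informative.

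The arms are known and differ in route of administration. Section 3.2 defends the open-label design by pointing to a common assessment schedule in both arms. That safeguard ends with treatment, because scanning is then at the physician's discretion and could depend on knowledge of the arm. The quantity exposed is the PFS hazard ratio, to which Section 12.1 attaches its two numerical thresholds.

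**Working it through.** There is no plan figure to reproduce: Section 12.2 fixes n = 40 by external constraints and gives no event count, dropout rate or rate of stopping without progression. The check is one of text and timing, followed by an illustration of size.

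**1. What counts after stopping.** Three things still produce a PFS event:
- progression on an optional scan within 6 months of the previous assessment;
- clinical progression in non-measurable disease (Section 6.3, and the change-in-therapy criterion in 6.3.4);
- death within 6 months of the last assessment.

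Without any of these, the patient is censored at the last tumor assessment. An optional scan without progression moves that date forward. If none is done, the date is that of the last on-treatment scan. The documents do not say whether progression learned by phone is an event.

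**2. Timing against the 6-month rule.** Two 28-day cycles are 8 weeks, so the last on-treatment scan is normally 0 to 8 weeks before stopping. Contacts come about 13 and 26 weeks after stopping.
- First contact: 13 + 0 to 13 + 8 = 13 to 21 weeks after the last scan, inside 26 weeks.
- Second contact: 26 + 0 to 26 + 8 = 26 to 34 weeks, at or beyond the limit.

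So only about one routine contact falls clearly inside the window, and it need not include a scan.

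**3. Size (illustrative).** From the documents: 20 per arm, 8-weekly scans and at least 6 months of follow-up. Assumed: exponential PFS with equal hazards in both arms while on treatment; median 4, 6 or 11 months; follow-up uniform over 6 to 24 months; later hazard of patients who stop multiplied by 1 or 2. A share p stops before progression, with stopping hazard μ = λp/(1 − p), where λ = ln 2/median. Deaths are not modelled separately. In the no-scan scheme no stopper is rescued by an optional scan, so it is the adverse extreme. There were 3,000 replicates per setting.

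With 20% stopping in each arm (0.20 × 40 = 8 patients):

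| Median PFS (months) | Later hazard | Events, no scans after stopping | Events, scans continue | Lost |
|---|---|---|---|---|
| 4 | ×1 | 29.4 | 34.9 | 5.5 |
| 4 | ×2 | 29.2 | 35.9 | 6.7 |
| 6 | ×1 | 26.5 | 30.6 | 4.1 |
| 6 | ×2 | 26.5 | 31.8 | 5.3 |
| 11 | ×1 | 20.6 | 22.6 | 2.0 |
| 11 | ×2 | 20.5 | 23.6 | 3.1 |

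The loss is about 2 to 7 events. The median fitted hazard ratio lies between 0.99 and 1.01 under both schemes.

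With unequal stopping (10% in one arm, 30% in the other), the largest gap between schemes occurs at median 6 months, 30% in the fulvestrant arm and later hazard ×2. The hazard ratio is 1.02 without scans and 1.09 with them (difference 0.07). P(HR < 0.8) is 0.251 and 0.166 (difference 0.085, about 0.09). The direction is not fixed: with the 30% in the tamoxifen arm instead, the hazard ratios are 0.97 and 0.91.

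**4. Background imprecision.** With d events and a true hazard ratio of 1, P(fitted HR < 0.8) = Φ(ln 0.8 ÷ (2/√d)).
- d = 20: Φ(−0.223/0.447) = 0.31.
- d = 40: Φ(−0.223/0.316) = 0.24.

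**The case against.** **Censoring is not automatic.** A reader might infer that everyone who stops without progression is censored at the last on-treatment scan. The documents do not support that: the rule refers to the last tumor assessment of any kind, and the three routes in step 1 remain open. Table 4 also marks physical examination and medical history as required in Follow Up until death, although that sits awkwardly with footnote n's phone option. This stands; the problem is a default path.

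**Record review can yield radiology.** PFS rests on local reading, and a local CT report can be found in the records. This also stands. The gap is that nothing requires such scans to be retrieved and read by RECIST.

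**Other anticancer therapy.** Section 5.3 item 3 says that if another agent is needed "then the patient must first be withdrawn from the study". A reader might infer that follow-up then ends. Section 5.8 points the other way, seeking permission for continued follow-up, but it speaks of withdrawal at the patient's request. The texts need reconciling; they do not establish that follow-up is cut off.

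**A large bias.** A reader might infer one from a simulation (20 per arm, equal exponential PFS with median 4 to 9 months, 24-month accrual plus 6 months) that censors 20% of true events in the fulvestrant arm, and none in the tamoxifen arm, at the preceding scan. It gives a median hazard ratio of 0.81 to 0.83 and P(HR < 0.8) of 0.46 to 0.49. That builds the answer in: only patients about to progress are lost, none is rescued, and all are in one arm. If 20% of one arm instead stop at a random time before progression, with later hazard ×1 or ×2, the median is 1.00 to 1.05 and the probability 0.22 to 0.29, against 0.25 to 0.27 with no loss. Neither that version nor step 3 links the time of stopping to prognosis, so stronger bias cannot be excluded; the documents give no basis for assuming it.

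**Rarity and rank.** Section 5.2.3 treats early discontinuation of the endocrine drugs as unusual, palbociclib is in both arms, PFS is secondary and the primary objectives are descriptive. This limits the weight of the point but does not remove it.

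**Conclusion.** The concern holds as a gap between intent and schedule. Sections 5.6, 5.8 and 6.3.4 want outcomes followed and objective progression documented after treatment stops; Table 4 and footnote n require no assessment that would do so. The default is avoidable and possibly informative censoring in the hazard ratio that Section 12.1 compares with 0.8 and 0.65.

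The size is uncertain and rests on assumed stopping rates. At 20% per arm it is about 2 to 7 events out of roughly 23 to 36, with little shift in the hazard ratio when stopping is balanced. At 10% versus 30% the shift is up to about 0.07, in either direction. The 0.8 threshold is imprecise in any case, being met 24% to 31% of the time under no effect with 20 to 40 events. The plan should be corrected, but the gap does not undermine the trial's descriptive primary aims.

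**What to change.** - Reconcile Table 4 and footnote n with Sections 5.6, 5.8, 6.3.4 and 11.1. For patients who stop without progression, have sites submit every scan done as standard of care, including those found by record review, for local RECIST reading until progression, death or withdrawal of consent to follow-up.
- State that progression reported by phone counts only when backed by a scan report or by the Section 6.3 criteria for non-measurable disease.
- Add to Section 12.1 a PFS sensitivity analysis that counts progression or death after treatment stops as an event, including events beyond the 6-month gap.
- Reconcile the withdrawal wording in Section 5.3 item 3 with the follow-up described in Section 5.8 and footnote n.

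The cost is document wording and modest extra data collection: about 4 to 8 of 40 patients if 10% to 20% stop without progression (0.10 × 40 = 4; 0.20 × 40 = 8). Making 8-weekly CT mandatory after treatment would close the gap more fully, but it adds a procedure and burden for patients off study drug. The point does not depend on it.
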